Assessments. All assessments will be remote and accessible by smartphone, tablet, or computer. After confirming eligibility and consenting to participate, participants will be randomly assigned to one of the four study groups (Table 1) and study personnel will mail a welcome package including study information, a CoVita iCO personal smokerlyzer device, and NRT (for groups A and B only). Upon receipt of the welcome package, participants will complete a brief baseline survey on the internet (Table 2) and will be encouraged but not required to submit a baseline breath CO sample using the CoVita iCO device and iCOquit mobile application which is compatible with Mac iOS and Android operating systems for smartphones and tablets. We will not ask participants to return their personal CoVita iCO Smokerlyzer. All participants will be free to keep their personal CoVita iCO Smokerlyzer after the conclusion of their participation.

Table 2. Schedule of assessments

	Baseline	Daily 1 wk pre- and 1 wk post-quit	Weekly surveys and End of Tx	6-Month follow-up
Human subjects protocol form 1/25/2022				

Individual-level factors				
Socio-demographic information	x			
Tobacco use history & breath CO	x			
Motivation rulers for CC & EC cessation ¹²⁵	x		x ^a	x ^a
CC and EC dependence and demand				
CC Strong dependence questionnaire	x		x ^a	x ^a
EC Strong dependence questionnaire	x		x ^a	x ^a
Cigarette & e-Cigarette Purchase Tasks ¹²⁸	x		x ^a	x ^a
Minnesota Nicotine Withdrawal Scale ¹³¹	x		x	x
Intervention engagement & adverse effects				
Preference for quitting CCs only versus CCs + ECs simultaneously	x			
Frequency of EC use (groups A & C) or EC abstinence (groups B & D)		x	x	x
NRT use and perceived helpfulness (groups A & B)		x	x	
Responses to text messages and perceived helpfulness		x	x	
Study-related adverse effects		x	x	x
Outcomes				
Primary: CO-verified 7-day point prevalence CC abstinence			x	x
Secondary:				
CO-verified 30-day CC abstinence			x	x
Self-reported attempts to quit CCs		x	x	x
Cigarettes per day	x	x	x ^a	x ^a
Time to first CC after waking ¹³² and CC addiction ladder	x	x	x ^a	x ^a

^aAssessed only among participants who relapsed or failed to quit CCs. CC=Combustible cigarettes; EC=Electronic cigarette; NRT=Nicotine replacement therapy; Tx=Treatment.

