Treatment. The consent form explains that a primary aim of this RCT is to test whether quitting versus continuing ECs is more effective when quitting CCs, and currently there is mixed evidence supporting both strategies. After randomization, all participants will receive information about the study including instructions to set a quit date and which product(s) to quit. Written instructions for the intervention will be provided and participants will also be asked to view a supplementary video presentation. We will provide participants in groups A and C with instructions to quit CCs but continue using ECs with the rationale that ongoing use of ECs could help them abstain from CCs. Specifically, we will instruct participants in groups A and C to use ECs in place of CCs to help cope with cravings or urges to smoke CCs. In contrast, participants randomized to conditions B and D will receive instructions to quit CCs and quit ECs with the rationale that quitting ECs could help them abstain from CCs. We will instruct participants in groups B and D to abstain from vaping because ECs could trigger relapse to CCs. Participants in groups A and B will also receive instructions for how to use NRT.

Participants randomized to conditions A and B will be mailed 3 one-month supplies of dual 14 mg NRT patches and 4 mg mini-lozenge because this appears to be the most effective non-prescription medication combination for smoking cessation.¹⁴⁰ However, participants will have the option to stop receiving NRT from the study. Participants will be instructed to start using both forms of NRT 2 weeks prior to their quit date because pre-quit NRT appears to increase the effectiveness of NRT.¹⁴¹ Further, the recommended use for the NRT has recently been changed to incorporate use while smoking because "the FDA has determined that there are no significant concerns with using NRT products at the same time as another nicotine-containing product like a cigarette (<https://www.nicodermcq.com/faq.html>)."¹⁴² We will instruct participants to use one patch per day and use mini-lozenges when they have cravings to smoke CCs (condition A) or cravings to smoke CCs or use ECs (condition B), without surpassing 24 mini-lozenges in one 24-hour period. Anyone for whom NRT is contraindicated will be excluded from the proposed RCT. In addition, though risk of serious adverse events from NRT is low (eg.¹⁴²), we will assess adverse events related to study procedures on weekly surveys.

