Statistical methods. Baseline participant characteristics, including socio-demographic information and tobacco use history, will be compared between the four conditions using analyses of variance for continuous and chi-square tests for categorical variables. Differences between conditions at baseline will be considered as potential covariates in subsequent analyses. Consistent with the intent-to-treat approach,¹⁵² our primary analysis will include all randomized participants who complete the baseline survey, independent of early dropout. Participants who are missing abstinence data will be assumed to be smoking. Missing survey data on other outcomes will be imputed using multiple imputation.¹⁵³ For our Aim 1 primary outcome, we will compare the proportion of participants who achieved CO-verified (< 6 ppm) 7-day point-prevalence abstinence at the end of treatment between conditions that were provided NRT versus no NRT using logistic regression. For our Aim 2 primary outcome we will compare the proportion of participants who achieved CO-verified 7-day point-prevalence abstinence at the end of treatment between conditions assigned to quit CCs only versus quit CCs and Ecs simultaneously. For our Aim 3 primary outcome we will compare the conditions assigned to quit CCs only versus quit CCs and Ecs simultaneously on 1) the proportion of participants who report a serious study-related adverse event using a chi-square test and 2) the total number of reported study-related adverse events during the treatment period using a t-test or nonparametric test, depending on the distribution. In addition, we will conduct an exploratory analysis using logistic regression to examine the interaction between the treatment arms (NRT versus no NRT by continue EC versus quit EC) with CO-verified 7-day point-prevalence abstinence as the outcome. We will also examine the effect of EC continuation versus NRT on CC abstinence by comparing Group B (quit CCs and Ecs with NRT) versus Group C (quit CCs and continue Ecs without NRT) using logistic regression. We will conduct a series of sensitivity analyses using 30-day abstinence at the 6-month follow up as the outcome and test condition as a predictor of time to relapse after quit day using Cox proportional hazards regression survival analyses. Finally, we will conduct sensitivity analyses when missing data are treated as missing.

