Additional secondary analyses will explore moderators and intervention effects on relevant smoking outcomes. For example, we will test days of NRT use as a moderator of NRT's effect on abstinence using logistic regression. Similarly, we will test days of EC use as a moderator of the effect of being assigned to continue versus quit Ecs on CC abstinence using logistic regression. We will assess baseline preference for continuing versus quitting Ecs as a moderator of the effect of being assigned to continue versus quit Ecs on CC abstinence using logistic regression. Among participants who fail to quit CCs, we will examine condition as a predictor of change in amount of CC use, self-reported attempts to quit CCs, nicotine dependence, self-efficacy to quit CCs, and motivation to quit CCs. Analyses will be performed using SAS Statistical Software V9.4 (SAS Institute, Cary, NC). Statistical significance will be determined based on p<.05 for all analyses.

Sample size justification. We propose recruiting, consenting, and randomizing a sample of 390 participants. Given the high rate of fraudulent responses in remote studies, we anticipate that we will need to consent 1,030 individuals in order to verify the identification and randomize 390 participants. Based on prior remote tobacco treatment research among young adults,³³ we estimate 80% retention of randomized participants and thus anticipate retaining 312 participants by the end of treatment when we will assess our primary outcome. This proposed sample size is based on having sufficient power for detecting group differences on the primary outcome of 7-day point-prevalence abstinence at the end of treatment (i.e., week 12) for the treatment comparisons in Aims 1 and 2. A sample size of 78 in each of the 4 treatment groups will give over 90% power to detect a difference between NRT and No NRT and 80% to detect a difference between CC+CE and CC only in 7-day point-prevalence abstinence rates, assuming overall rates of 31% in the NRT and 12% in the No NRT group and overall rates of 15% in the CC+CE and 28% in the CC only group with $\alpha=.05$. While we know of no prior trials of NRT for young adults or smoking cessation treatment for dual users, these estimates are based on relevant prior trials of NRT or text messages for smoking cessation.^{37,69,140,154}

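### Preference and other baseline measures are collected after randomisation and delivery of the study package, so they may already reflect the assigned arm when used as moderator or covariates

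*Combined protocol and SAP*

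**What the plan says.** **Order of events.** Under Procedures, Assessments, once eligibility and consent are settled, "participants will be randomly assigned to one of the four study groups (Table 1) and study personnel will mail a welcome package". The package holds study information, a CO device and, for groups A and B only, NRT. The survey comes next: "Upon receipt of the welcome package, participants will complete a brief baseline survey on the internet". At the same point participants "will be encouraged but not required to submit a baseline breath CO sample".

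**What that survey contains.** Table 2 schedules at baseline the preference item (quit CCs only, or both products), the motivation rulers, the CC and EC dependence questionnaires, the purchase tasks, the withdrawal scale, tobacco use history and CO. Preference is asked at no other time.

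**When the EC arm is disclosed.** Under Treatment: "After randomization, all participants will receive information about the study including instructions to set a quit date and which product(s) to quit". The instructions argue for the assigned strategy. Groups A and C are told that ECs could help them stay off CCs, and groups B and D that ECs could bring on relapse. Whether this reaches participants before or after the baseline survey is not stated.

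**How the data are used.** Statistical methods compares baseline characteristics across the four conditions and adds: "Differences between conditions at baseline will be considered as potential covariates in subsequent analyses". The secondary analyses then use preference: "We will assess baseline preference for continuing versus quitting Ecs as a moderator of the effect of being assigned to continue versus quit Ecs".

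**The concern.** A moderator, or a covariate used to adjust a treatment comparison, should be fixed before treatment can act on it. Here the measures are taken after assignment, at a time when participants may know it.

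- **Moderator.** Someone who has just been given reasons to continue ECs, or to stop them, may state a preference that echoes those reasons. The analysis is meant to show whether matching the EC strategy to prior preference matters. It would then partly describe response to the assignment.
- **Covariates.** A rule that looks for differences between conditions is more likely to pick the variables that assignment has moved. Adjusting for such a variable shifts the treatment coefficient away from the effect of assignment.
- **NRT factor.** The package itself shows A and B that they have NRT. NRT is to start two weeks before the quit date. The daily surveys run one week either side of that date and fall in weeks 2 and 3, so the quit date is near the end of week 2 and NRT starts at about study start. Withdrawal, dependence and CO in A and B could therefore already reflect NRT use.

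**Working it through.** **Plan's own figures.** The plan gives no figure on this point, only power. With 78 per group, each factor level has 156. A two-sided pooled two-proportion calculation at alpha .05 gives 98.6% for 31% vs 12% (plan: over 90%) and 80.1% for 28% vs 15% (plan: 80%). Also 312/0.8 = 390. These reproduce, and the fix does not alter them.

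Everything below is illustration. The shift sizes are assumptions because the documents give none.

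**1. Would a shift in preference show as a baseline difference?** Assume a true 50/50 split and let a fraction s answer according to their EC arm, whatever their real view.

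- Stated preference to continue is (1 − s) × 0.5 + s in A/C and (1 − s) × 0.5 in B/D.
- At s = .20 this is 0.60 and 0.40. Half of that 20% already agreed with their arm, so only 10% of participants change their answer.
- For the plan's four-condition chi-square with 390/4 = 97.5 per group, X² = 390 × d²/0.25, where d is each group's distance from 50%. At d = 0.10, X² = 390 × 0.01/0.25 = 15.6 on 3 df, p = .0014.

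Over a range of s (chance of p < .05 from the noncentral chi-square on 3 df, with X² as noncentrality):

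| s | A/C vs B/D | X² (3 df) | p | Chance of p < .05 |
|---|---|---|---|---|
| .10 | 55% vs 45% | 3.9 | .27 | 35% |
| .20 | 60% vs 40% | 15.6 | .0014 | 93% |
| .30 | 65% vs 35% | 35.1 | < .001 | > 99% |

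With preference measured before assignment the chance is 5%.

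**2. What happens to the moderator?** Take the plan's 28% (continue) and 15% (quit) as base rates and a true interaction log-OR of 1.0: being matched to one's preference adds 0.25 to the logit and being unmatched subtracts 0.25. Assume switching is unrelated to outcome. At s = .20:

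- Continue arm: true abstinence is 33.3% if matched and 23.2% if unmatched. Those stating continue show (0.5 × 33.3 + 0.1 × 23.2)/0.6 = 31.6%, and those stating quit show 23.2%.
- Quit arm: 18.5% if matched and 12.1% if unmatched. Those stating quit show (0.5 × 18.5 + 0.1 × 12.1)/0.6 = 17.4%, and those stating continue show 12.1%.
- Observed interaction = [logit(.316) − logit(.121)] − [logit(.232) − logit(.174)] = 1.21 − 0.36 = 0.85.

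At s = .10 and .30 it is 0.92 and 0.79. With no true interaction, none is created.

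**3. What happens to an adjusted estimate?** Assume a prognostic score with log-OR 0.5 per SD, moved by assignment in the arm with the higher abstinence, and abstinence of 28% vs 15%. The adjusted OR is about 2.28 × exp(−0.5 × shift), where 2.28 is the conditional OR. Simulation gives 2.26 with no shift and:

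| Shift (SD) | Formula | Simulated adjusted OR |
|---|---|---|
| 0.1 | 2.17 | 2.16 |
| 0.2 | 2.06 | 2.08 |
| 0.3 | 1.96 | 1.98 |
| 0.5 | 1.78 | 1.77 |

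The unadjusted OR is (.28/.72)/(.15/.85) = 2.20 whatever the shift. A shift of opposite sign inflates the adjusted OR instead: at 0.2 SD, 2.28 × exp(0.1) = 2.52.

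**The case against.** The strongest reply is that the step that matters most for preference is undocumented. The only stated arm difference in the package is NRT, and that does not reveal the EC arm. The EC instructions might come after the survey, and the timeline figure is not available to settle it. This stands, and it limits the claim to possible contamination. It does not remove the point, because nothing in the plan prevents earlier disclosure.

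Three stronger readings are tempting, and the documents do not support them.

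- **That the moderator analysis is void.** Disclosure before the survey is not established. Even with it, switching unrelated to outcome dilutes the interaction (1.0 to between 0.92 and 0.79) without creating one. If the more motivated were the ones to switch, a false matching effect could arise, but the documents give no basis for sizing it. The analysis is also exploratory.
- **That the plan will adjust for a shifted variable.** Covariates are only to be considered. The characteristics named are socio-demographics and tobacco use history, which assignment can hardly change, although the list is open. Table 2 files preference under intervention engagement, so its entry into the baseline comparison is itself an assumption.
- **That the primary Aim 1 and Aim 2 results are biased.** An unadjusted comparison is untouched by this route. The preference illustration runs along the EC factor and says nothing about Aim 1. For Aim 1 the possible path is through NRT already in hand, and perhaps in use, and no shift there has been quantified.

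Some protection already exists. Eligibility screening records cigarette use, EC days and the wish to quit before randomisation, and consenting participants' screener answers are kept in the research record.

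**Conclusion.** The concern holds as a risk built into the order of procedures. The survey follows randomisation and package receipt; this is explicit, and no section contradicts it. Whether assignment has moved the answers depends on the unstated timing of the EC instructions and on an unknown shift.

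Under the assumed shifts, a 10% rate would usually pass unnoticed in the four-condition test (35% chance of p < .05) and a 20% rate would usually be flagged (93%). The moderator would be diluted by roughly 8% to 21% on the log-odds scale for shifts of 10% to 30%. An adjusted OR of 2.26 could fall to 2.08 at 0.2 SD or 1.77 at 0.5 SD, or rise if the shift ran the other way.

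The exposed variables are preference, motivation, dependence, withdrawal, purchase tasks, recent use and CO. Fixed demographics and screener items are not exposed. Who enters the analysis set is a separate matter. The change should be made before enrolment, because prior preference cannot be recovered once participants have seen their assignment.

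**What to change.** 1. **Assessments.** After consent and before allocation, collect preference, the motivation rulers, CC and EC dependence, withdrawal, and recent CC and EC use. The ID-verification call, or a survey linked to it, suits this: the sample size section has identity verified after consent and before randomisation, and the call is already paid. The online screener is less suitable because it precedes consent and would put research scales to many people who never enrol.
2. **Assessments and Treatment.** State that the allocation and the EC instructions are released only after those items are submitted. The first CO sample needs the mailed device and can stay after delivery, but should then not serve as an adjustment covariate.
3. **Statistical methods.** Restrict covariates to data collected before randomisation, including screener data, and name them in advance.
4. **Secondary analyses.** Use the pre-randomisation preference as the moderator.

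**Cost.** Existing questions move to an existing contact. The pre-randomisation step becomes longer, and some candidates will be lost before allocation. There is no new visit, and N = 390 and the planned power stay as they are.

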Using a 2x2 factorial design (Table 1), young adults who smoke CCs and use ECs will be randomly assigned to one of four conditions: A) NRT plus text messages to quit CCs only, B) NRT plus text messages to quit CCs and ECs simultaneously, C) text messages alone to quit CCs only, or D) text messages alone to quit CCs and ECs simultaneously. We will recruit, consent, and randomize 390 participants with the aim of retaining 312 (80%) by the end of treatment. Participants in each condition will complete a survey at baseline, weekly surveys throughout the 3-month treatment period, brief daily surveys for one week before and one week after the assigned quit date, an end of treatment survey, and a survey at a follow-up 6 months after treatment began (Figure 1). In addition, participants will be encouraged but not required to submit breath CO samples at baseline, all weekly surveys, the end of treatment, and the 6-month follow-up using the CoVita iCO personal smokerlyzer (<https://www.covita.net/ico-overview/>).

Table 1. 2x2 factorial design

Nicotine replacement therapy (NRT)	Text-messages to quit CCs only vs quit CCs & ECs	
	Quit CCs & continue ECs	Quit CCs & quit ECs
Yes	A) NRT & text messages to quit CCs & continue ECs	B) NRT & text messages to quit CCs & quit ECs
	C) Text messages alone to quit CCs & continue ECs	D) Text messages alone to quit CCs & quit ECs

[figure not shown]

Figure 1. Timeline of study procedures. CC=Combustible cigarettes; EC=Electronic cigarette; NRT=Nicotine replacement therapy.

Procedures: Describe all procedures (sequentially) to which human participants will be subjected. Identify all procedures that are considered experimental and/or procedures performed exclusively for research purposes. Describe the types, frequency and duration of tests, study visits, interviews, questionnaires, etc.

Note: A clinical research protocol may involve interventions that are strictly experimental or it may involve some aspect of research (e.g., randomization among standard treatments for collection and analysis of routine clinical data for research purposes). It is important for this section to distinguish between interventions that are experimental and/or carried out for research purposes versus those procedures that are considered standard therapy. In addition, routine procedures performed solely for research purposes (e.g., additional diagnostic/follow-up tests) should be identified.

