Participants will be informed about possible Aes in the consent. At study onset, participants will be provided with a phone number and e-mail to report any Aes that are urgent. We will withdraw participants who have an FDA-defined serious AE (SAE) that are likely or probably related to the study procedures as well as participants who become pregnant or begin breast feeding. Traditional methods of collecting Aes can be insensitive, thus we will inquire about Aes weekly during the 3-month study period and instruct participants to contact research personnel if they experience a severe AE. We will also assess whether participants have become pregnant or started breastfeeding on weekly questionnaires during the treatment period. Any participant who indicates they became pregnant or began breastfeeding during the treatment period will be withdrawn from the study and provided with a referral to tobacco treatment. In addition, we will encourage participants to contact research personnel if they have questions about withdrawal symptoms or believe any withdrawal symptoms require treatment. A study licensed medical provider will be available by phone to discuss any questions about withdrawal symptoms or Aes.

Potential participants are free not to participate in this study and participants are free to withdraw at any time. Potential participants who screen ineligible or do not consent to participate will be provided with resources to help them quit smoking outside of this study.

3. Potential Benefits to Participants and Others

The primary potential benefit to participants is that they may quit smoking cigarettes. People who smoke cigarettes have approximately a 50% chance of dying from smoking-related illness. Participation in this study could increase the chances of smoking cessation and prevent long-term morbidity and mortality from cigarettes. This research also stands to provide scientific benefit by improving understanding of the influence of NRT and continued EC use during a smoking cessation intervention. Further, the smoking cessation intervention for young adult dual users tested in this research has the potential to benefit public health by decreasing the substantial personal and societal costs associated with tobacco use in the United States. Thus, we believe the risks to participation in the proposed research are reasonable in relation to the anticipated benefits.

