Yes No NA

If yes, how often?

Adverse Event, Unanticipated Problem (UAP), Reportable New Information (RNI): Describe how events and UAPs will be evaluated and reported to the IRB. All protocols should specify that, in the absence of more stringent reporting requirements, the guidelines established in the "Adverse Event and Unanticipated Problems Reporting Policy" will be followed. The UVM/UVM Medical Center process for review of adverse events and UAPs to subjects or others should be included in the DSMP.

The guidelines established in the Committees on Human Research "Adverse Event and Unanticipated Problems Reporting Policy" will be followed.

Withdrawal Procedures: Define the precise criteria for withdrawing subjects from the study. Include a description of study requirements for when a subject withdraws him or herself from the study (if applicable).

We will withdraw participants if we think it is harmful for them to participate (e.g., if they experience an SAE related to study procedures) or if we believe the information they are providing us is not valid. Participants will be free to withdraw at any time and will be provided with email and telephone contact information for study personnel to communicate if they would like to be withdrawn from the study.

Sources of Materials: Identify sources of research material obtained from individually identifiable human subjects in the form of specimens, records or data. Indicate whether the material or data will be obtained specifically for research purposes or whether use will be made of existing specimens, records or data.

Computerized surveys from baseline, weekly, 3-month and 6-month surveys as well as results from participants' personal iCO Smokerlyzers will be obtained specifically for research purposes. In addition, data from daily surveys during weeks two and three of the treatment period will be obtained specifically for research purposes.

DRUG INFORMATION

Investigators are encouraged to consult the UVM Medical Center Investigational Pharmacy Drug Service ([name]) prior to finalizing study drug/substance procedures.

Drug (s)

Not applicable

Drug name – generic followed by brand name and common abbreviations. Availability – Source and pharmacology; vial or product sizes and supplier. If a placebo will be used, identify its contents and source.

Nicotine replacement therapy (NRT)

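### Withdrawal for pregnancy, breastfeeding or a related SAE ends study participation, not only treatment, with no stated outcome follow-up; those withdrawn early would, on the natural reading, count as smoking

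*Combined protocol and SAP*

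**What the plan says.** Protection against Risk has pregnancy and breastfeeding asked about on the weekly questionnaires. Anyone who reports either during treatment "will be withdrawn from the study and provided with a referral to tobacco treatment". The rule draws no line between stopping NRT and leaving the study, and it covers the two groups that receive no NRT.

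The same section says of SAEs: "We will withdraw participants who have an FDA-defined serious AE (SAE) that are likely or probably related to the study procedures". Withdrawal Procedures is more discretionary: "We will withdraw participants if we think it is harmful for them to participate", with a related SAE given as an example and invalid information as a second ground. The adverse event text under Procedures leaves withdrawal after a severe problem to consultation with the medical provider.

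None of these sections, nor the assessment and retention text, provides for 3-month or 6-month outcomes after withdrawal. Reporting mechanisms of AEs and SAEs follows SAEs medically until they resolve or stabilise, but that is not abstinence follow-up.

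Statistical methods includes every randomized participant with a baseline survey in the primary analysis, regardless of early dropout. It then states: "Participants who are missing abstinence data will be assumed to be smoking". It adds that "we will conduct sensitivity analyses when missing data are treated as missing".

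**The concern.** Stopping an intervention and stopping outcome collection are different decisions, and an intent-to-treat analysis depends on keeping them apart. Here the protocol itself ends follow-up, and the analysis rule then supplies an outcome. A participant who quits and is withdrawn at week 6 for pregnancy would be scored as smoking at week 12.

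Unlike ordinary dropout, this loss can be avoided. All follow-up is by remote survey, the CO device has been mailed and is the participant's to keep, and a survey or breath sample needs neither NRT nor text support. What is at stake is a few obtainable primary outcomes being replaced by assumed ones, together with the 6-month outcomes of the same people.

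For Aim 3, a related SAE is already on record when it triggers withdrawal. The second Aim 3 measure, "the total number of reported study-related adverse events during the treatment period", can be cut short for anyone withdrawn early.

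**Working it through.** **Inputs from the documents.** 390 randomized; 80% retention; 312 retained (Sample size justification). About 80% women (Inclusion of Women). Planning abstinence rates of 28% vs 15% for Aim 2 and 31% vs 12% for Aim 1; alpha 0.05, taken as two-sided.

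**Inputs assumed.** The documents give no pregnancy rate. I take 0.5% to 3% of women over 12 weeks, equal across arms. The upper end is probably too high, because Inclusion/Exclusion Criteria exclude women who are pregnant, planning pregnancy, or sexually active with a male partner without protection or birth control. No SAE rate is given, so none is estimated.

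**The plan's own figure.** The plan sets out "A sample size of 78 in each of the 4 treatment groups", which is 156 per factor level. With the pooled-variance normal formula,

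power = Φ{[√n·|p1 − p2| − 1.96·√(2·p̄(1 − p̄))] / √[p1(1 − p1) + p2(1 − p2)]},

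28% vs 15% with n = 156 and p̄ = 21.5% gives 0.801, and 31% vs 12% gives 0.986. The stated 80% and over 90% are reproduced, and 312/0.80 = 390.

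**Number withdrawn.**
- Women: 390 × 0.80 = 312.
- Withdrawn: 312 × 0.005 = 1.56 to 312 × 0.03 = 9.36, so about 2 to 9.
- Share of all randomized: 1.56/390 = 0.4% to 9.36/390 = 2.4%.
- If 20% of these would have been lost anyway: 1.56 × 0.80 = 1.25 to 9.36 × 0.80 = 7.49.

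**Quitters mis-scored.**
- Mean planning rate for Aim 2: (28% + 15%)/2 = 21.5%.
- Gross: 1.56 × 0.215 = 0.34 to 9.36 × 0.215 = 2.01.
- Net of 20% loss: 1.25 × 0.215 = 0.27 to 7.49 × 0.215 = 1.61.
- CO samples are optional ("participants will be encouraged but not required to submit breath CO samples"), so follow-up would not verify every quitter. If an assumed 50% to 90% sent one, the recoverable number is 0.27 × 0.5 = 0.13 to 1.61 × 0.9 = 1.45.

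**Illustrative effect on the comparisons.** If the withdrawals come on top of everything already planned for, both rates are multiplied by (1 − share).
- Aim 2 difference: 13 × 0.004 = 0.05 to 13 × 0.024 = 0.31 points lost.
- Aim 1 difference: 19 × 0.004 = 0.08 to 19 × 0.024 = 0.46 points lost.

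| Comparison | Per side | Power as planned | Share 0.4% | Share 2.4% |
|---|---|---|---|---|
| Aim 2 | 156 | 0.801 | 0.799 | 0.789 |
| Aim 2 | 195 (all 390 analysed) | 0.881 | 0.879 | 0.871 |
| Aim 1 | 156 | 0.986 | 0.985 | 0.983 |

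The power rows are upper limits on the effect under these assumptions, for the reason given in the objection.

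**The case against.** The strongest objection is that the point is immaterial: one or two mis-scored quitters among 390 cannot move any aim. That stands, and it is why this is a cheap improvement and not a flaw in the primary analysis.

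**Power.** A reader might infer that the rule costs Aim 2 one or two points of power. The documents do not support that. The 156 per side are participants retained after a planned 20% loss, and nothing in Sample size justification says protocol withdrawals fall outside that allowance; subtracting them again may count them twice. The 195-per-side row has the same weakness. It assumes that 28% and 15% already reflect missing scored as smoking, in which case these withdrawals may be included too. If the rates instead describe retained participants, scoring the planned loss as smoking gives 28% × 0.80 = 22.4% vs 15% × 0.80 = 12%, and power of about 0.78 before any pregnancy.

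**Scoring.** A reader might infer that the plan says withdrawn participants are coded as smoking. It never does. The coding follows from reading the withdrawal rule together with the missing-data rule, and the consent form may provide for follow-up. Someone who first reports a pregnancy on the end-of-treatment survey may also have given the primary outcome already.

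**Bias against an arm.** A reader might infer that SAE withdrawals penalise NRT. There is no rate behind that: the protocol calls serious events with NRT very rare, and Hypothesis 3 expects no difference by EC assignment. Pregnancy withdrawal applies equally in all four groups.

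**Breastfeeding.** Eligibility excludes women who are pregnant, breastfeeding or planning to breastfeed within 3 months, so onset within 12 weeks would be rare.

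**Existing safeguard.** The sensitivity analysis with missing treated as missing does not score these participants as smoking. It omits them, however, and does not recover their outcomes. What survives is narrow: the rule as written gives up outcomes that could be collected.

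**Conclusion.** The point holds as a small, avoidable weakness. Withdrawal for pregnancy, for breastfeeding (rarely) or for a related SAE is written as withdrawal from the study, and the review copy provides for no outcomes afterwards. Unless the consent form says otherwise, those withdrawn before the end-of-treatment survey would on the natural reading be analysed as smoking whatever their true status.

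The size is very small: about 2 to 9 pregnancy withdrawals and at most about 1 to 2 mis-scored quitters. This rests on the assumed 0.5% to 3% pregnancy rate, the anticipated 80% women and the planning abstinence rates. No main conclusion is expected to change. Confidence is medium, because the coding is inferred and the consent form was not seen.

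**What to change.** Leave the clinical decision to stop treatment as it is. In Protection against Risk and Withdrawal Procedures:

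- Replace withdrawal from the study with withdrawal from the study intervention (NRT and text support) for pregnancy, breastfeeding and related SAEs. Keep full withdrawal for invalid information or withdrawn consent.
- State that, unless consent is withdrawn, the adverse event questions and the 3-month and 6-month surveys and CO samples continue.
- In Statistical methods, state that these participants are analysed as randomized on their observed outcome, with missing scored as smoking only if no outcome is obtained.

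If the consent form already provides for this, one sentence in Withdrawal Procedures is enough. Removal for high EC use is a separate rule and is not counted here, though the same sentence could cover it.

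The cost is protocol and consent wording, IRB agreement to survey follow-up of pregnant participants, and surveys and gift cards for a few people.
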